1. INTRODUCTION AND BACKGROUND

The mHealth Screening to Prevent Strokes (mSToPS) study is designed to determine whether mobile health monitoring can detect previously undiagnosed asymptomatic atrial fibrillation more effectively and lead to a reduction of thromboembolic events compared with usual care in a high-risk cohort identified and tracked using claims data.

The overarching objective of this study is to demonstrate that screening select individuals in their homes using wearable sensor technology can identify individuals with asymptomatic atrial fibrillation and that doing so will influence treatment and clinical outcomes.

Atrial Fibrillation Detection Objectives

- Identify a high-risk cohort optimized for screening based on claims data information.
- Determine the relative benefit of active screening compared to routine care (i.e., standard of care as defined by the medical care each patient is already receiving) for identifying new cases of atrial fibrillation after 4 months in the randomized cohort, and at one year in the combined monitored cohorts versus the matched observational control cohort
- As an exploratory analysis, compare the diagnostic capability of two different methods of rhythm screening – time-limited patch ECG monitoring versus long-term wearable pulse wave monitoring through photoplethysmography – for AF detection and tolerability.

Influence on Clinical Care

- Compare the rate of initiation of anticoagulation and other AF-specific therapeutic interventions (i.e. antiarrhythmic agents excluding beta-blockers and calcium channel blockers, cardioversions, ablation procedures or hospitalizations with a primary diagnosis of AF) at 12-months in the active monitoring cohort versus the matched observational control cohort.
- Compare the overall incremental costs of active monitoring for AF detection versus standard of care in the 3 years following the onset of monitoring.
- Identify the impact of active AF screening versus routine care on the time to first event of the following endpoints using claims data; A) among individuals diagnosed with new AF at 3 years following the initiation of screening, and B) the entire study cohort: utilizing claims data.
 - The combined endpoint of stroke/TIA, other systemic embolism, and/or myocardial infarction.

- In the Medicare population only, in who mortality data will be available, the combined endpoint of stroke/TIA, other systemic embolism, myocardial infarction and/or death

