3. ANALYSIS OBJECTIVES

The analysis objectives corresponding to the study objectives listed in 1. INTRODUCTION AND BACKGROUND are the following:

Primary Analysis

1. Compare incidence of newly diagnosed atrial fibrillation (as defined by ≥ 30 seconds of atrial fibrillation or flutter detected by device, or a new clinical diagnosis recorded in claims data) at the end of the 4-month monitoring period in the immediate monitoring cohort (n=1,000) with delayed monitoring cohort (control group) (n=1,000) using ICD-9/ICD-10 codes.

Secondary Analyses

1. Compare time to first event of newly diagnosed atrial fibrillation (as defined by ≥ 30 seconds of atrial fibrillation or flutter detected by device, or a new clinical diagnosis recorded in claims data) at the end of the 4-month monitoring period in the immediate monitoring cohort (n=1,000) with delayed monitoring cohort (control group) (n=1,000) using ICD-9/ICD-10 codes.
2. Compare incidence of newly diagnosed atrial fibrillation (as defined by ≥ 30 seconds of atrial fibrillation or flutter detected by device, or a new clinical diagnosis recorded in claims data) at the end of the 4-month monitoring period in the immediate monitoring cohort (intervention group) (n=1,000) with delayed monitoring cohort (control group) (n=1,000) using HPD definition.
3. Compare prevalence of atrial fibrillation in the actively monitored cohort (n=2,000) with the matched observational control cohort (n=4,000) at 12 months.
4. Compare time to event of newly diagnosed atrial fibrillation in the actively monitored cohort (n=2,000) with the matched observational control cohort (n=4,000) at 12 months.
5. Compare the rate of initiation of anticoagulation therapy in the actively monitored cohort with the matched observational control cohort at 12 months.
6. Compare the rate of initiation of other atrial fibrillation-related therapies (antiarrhythmic agents excluding beta-blockers and calcium channel blockers, cardioversions, ablation procedures or hospitalizations with a primary diagnosis of AF) in the actively monitored cohort with the matched observational control cohort at 12 months.
7. Compare utilization in actively monitored cohort with the matched observational cohort at 12 months.
8. Compare time to first event of the combined endpoint of stroke, systemic embolism, or myocardial infarction in the actively monitored cohort with the matched observational control cohort at 3 years:

- a. In the entire cohorts.

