Subjects randomized to the delayed monitoring cohort for the RCT will be actively monitored following completion of the 4 month RCT follow-up period (for which they serve as unmonitored controls). Subjects in the delayed monitoring group will receive their first Zio patch 4 months following their date of enrollment. The first Zio patch will be worn during the first two weeks of the 4-month monitoring period. A second Zio patch will be sent to subjects in the delayed monitoring group for wear during the final two weeks of the 4-month monitoring period.

Matched Observational Cohort Study: Actively Monitored (Immediate and Delayed) vs. Matched Observational Controls

For the Matched Observational Cohort study, the actively monitored group will include all subjects in the RCT who were randomly assigned to either active monitoring period (immediate or delayed).

Two matched controls will be selected for each of the 2,100 actively monitored subjects in the RCT (1,050 immediate + 1,050 delayed) from 1) the pool of subjects from the original eligible cohort who continue to be eligible based on monthly database updates and did not receive an invitation to enroll. Matching will be performed using the following criteria:

- Sex (exact)
- Age (exact by year of birth)
- CHA₂DS₂ VASc score (exact score)

CHA₂DS₂ VASc scores are re-calculated for monitored subjects at time of enrollment (updating scores calculated for eligibility of original pool). CHA₂DS₂ VASc scores are re-calculated for the pools of potential matched controls following the monthly update of the Aetna claims database and immediately prior to application of the matching protocol. Actively monitored subjects and controls will be matched on these updated CHA₂DS₂ VASc scores. Exact matches are prioritized. Matching of CHA₂DS₂ VASc score \pm 1 will be the next option if 2 exact match controls are not found for a monitored subject.

Start date for determination of outcomes from Aetna databases for both monitored subjects and matched controls will be the date of enrollment of the monitored subject. End date for the analysis of prevalence of atrial fibrillation, initiation of anticoagulation and initiation of other AF-specific interventions will be 12 months from the actively monitored subject's date of enrollment (by exact month and day). End date for analysis of outcomes at 3 years will be 3 years from the actively monitored subject's date of enrollment (by exact month and day).

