5. ENDPOINTS AND COVARIATES

[Data source in brackets]

Primary Endpoint

1. Atrial Fibrillation/Flutter: new diagnosis of atrial fibrillation or atrial flutter defined as:
 - a. ≥ 30 seconds of atrial fibrillation or flutter diagnosed and adjudicated on the iRhythm output (monitored cohort) [PI Diagnosis Database]
 - i. Date
 - ii. Duration
 - b. Claim for atrial fibrillation/atrial flutter with ICD-9 code 427.1 or 427.2 or ICD-10 code I48.91 or I48.9 [Aetna Claims Data; Aetna Medical Case]
 - i. Date

Secondary Endpoints

1. Atrial Fibrillation/Flutter: HPD algorithm [Aetna HPD Database]
2. Anticoagulation: Drug NDC codes for new refill for any:
 - a. Anticoagulant (dabigatran, rivaroxaban, apixaban) or
 - i. Date
 - b. P2Y12 Antagonists (clopidogrel, prasugrel or ticagrelor) without a new diagnosis of acute coronary syndrome
 - i. Date
4. Other AF-related therapies (i.e. antiarrhythmic agents excluding beta-blockers and calcium channel blockers, cardioversions, ablation procedures or hospitalizations with a primary diagnosis of AF)
5. UtilizationCommented [[name]]: Need to further define
3. Stroke-related visits during follow-up [Aetna Medical Case]
 - a. Inpatient
 - b. ER
 - c. Time to first stroke-related event (Inpatient or ER)
4. Myocardial infarction-related visits during follow-up [Aetna Medical Case]
 - a. Inpatient
 - b. ER
 - c. Time to first myocardial infarction-related event (Inpatient or ER)
5. Systemic thromboembolism-related visits during follow-up [Aetna Medical Case]
 - a. Inpatient
 - b. ER
 - c. Time to first systemic thromboembolism-related event (Inpatient or ER)
6. Death (Medicare population): [Aetna ATV; Aetna Membership Table]
 - a. Time to death (within 1 month of date)

- b. Cause of death
- 7. All-Cause Hospital Admissions [Aetna Medical Case]
 - a. Total number
 - b. Total length of stay
 - c. Individual admissions
 - i. Primary diagnosis
 - ii. Date
 - iii. Length of stay

Safety Endpoints

- 1. Hospital admission for primary bleeding diagnosis: [Aetna]
- 2. Incidence of non-AF, but other actionable heart rhythms captured by device (and confirmed by PI) [PI Diagnostic Database]
 - a. Atrial Tachycardia with variable block of > 30 seconds
 - b. Ventricular Tachycardia >5 beats
 - c. Pauses \geq 5 seconds
 - d. AV block
- 3. Early discontinuation of active monitoring in monitored cohort [Scripps Study Database]
 - a. Date of discontinuation
 - b. Cause of discontinuation

Exploratory Endpoint (Amiigo)

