The primary analysis will compare the proportion of subjects newly diagnosed with atrial fibrillation (numerator) per number of total number of subjects in the randomized group (denominator) during the first 4 months of the study between the immediate monitoring (intervention group) and delayed monitoring (control) groups using Fisher's exact test. Multivariable analysis of the primary outcome will also be performed using binomial multivariable logistic regression models to include baseline demographic (age, sex, race/ethnicity, median household income, geography, insurance type), and co-morbidity covariates. The primary analysis will be conducted with the endpoint (AF/atrial flutter) defined by any event in the Aetna databases with the ICD-9/ICD-10 code for AF/atrial flutter. Secondary analysis will be conducted using the same methods with the AF/atrial flutter endpoint defined by the HPD.

Intention-to-treat analysis will include all subjects who were randomized to the immediate monitoring or delayed monitoring groups and follow-up for outcomes from the device and the Aetna databases will be from date of enrollment to time of completion of monitoring with final patch or 4 months following enrollment, whichever is longest.

A per-protocol analysis will also be performed which will be limited to subjects in the immediate monitoring group who has a Zio patch reading of a total of at least 30 minutes and all subjects randomized to the delayed monitoring group.

Analysis of Matched Observational Cohort Study—12 month Follow-up

Analyses for the Matched Observational Cohort Study will involve comparison of outcomes in the actively monitored group from the randomized controlled trial (intervention = exposure to Zio patch monitoring) and the matched controls. Analysis at 12-month follow-up will include

the outcomes of new atrial fibrillation diagnosis and new prescriptions for 1) anticoagulants and 2) other AF-related medications.

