The analysis will compare the proportion of subjects with newly diagnosed atrial fibrillation (numerator) per number of total number of subjects in group (denominator) during the first 12 months from the date of enrollment of the actively monitored subject between the actively monitored cohort and matched observational cohort using Fisher's exact test. Multivariable analysis of the AF/atrial flutter outcome will also be performed using binomial multivariable logistic regression models to include baseline demographic (age, sex, race/ethnicity, median household income, geography, insurance type), co-morbidity covariates. The same analysis will be performed for the other 12-month follow-up outcomes of new prescription for anticoagulation medication and new prescription of other AF-related medications. All analyses will be conducted first as intention-to-treat and second among the per-protocol population.

Matched Observational Cohort Study – 3 year Follow-up

Analyses at 3 years of follow up will focus on time to event for disease outcomes (stroke, myocardial infarction, and systemic thromboembolism) and hospitalizations (all-cause and for bleeding) compared between the actively monitored cohort and the matched observational control cohort after 3 years of follow-up. Bivariate time-to-event analysis will be conducted using Kaplan-Meier analysis with the time to event calculated from the date of the enrollment of the actively monitored subject and the date of the first event of the specific disease outcome (separate analysis for each outcome). Subjects not having an endpoint event during the observation period will be censored at the end of the 3-year follow-up or date of discontinued enrollment from Aetna. Multivariable analyses will be conducted using Cox proportional hazard models and will include potential confounders including age, sex, race/ethnicity, insurance type, variables related to geography and co-morbidity scores. For the Cox models, if assumptions of proportionality are not met (as assessed by Kaplan-Meier and plots of Schoenfeld residuals), models accounting for non-proportionality (using time*covariate interaction terms) will be run.

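### SAP Section 7 analyses only new prescriptions for the 12-month outcome on other AF therapies, while Sections 1, 3 and 5 also include cardioversion, ablation and AF admissions

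*SAP*

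**What the plan says.** The SAP gives the content of this outcome in three places, and they agree.

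- Section 1, under influence on clinical care, lists antiarrhythmic drugs and then "cardioversions, ablation procedures or hospitalizations with a primary diagnosis of AF) at 12-months in the active monitoring cohort".
- Section 3, Secondary Analysis 6, calls for a comparison of the rate of starting "other atrial fibrillation-related therapies (antiarrhythmic agents excluding beta-blockers and calcium channel blockers, cardioversions, ablation procedures or hospitalizations with a primary diagnosis of AF", again at 12 months between the monitored and matched control cohorts.
- Section 5, among the secondary endpoints, has "Other AF-related therapies (i.e. antiarrhythmic agents excluding beta-blockers and calcium channel blockers, cardioversions, ablation procedures or hospitalizations with a primary diagnosis of AF".

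Section 4, which fixes the follow-up window, says that the end date for "initiation of anticoagulation and initiation of other AF-specific interventions will be 12 months" from the monitored participant's enrolment. Its term is interventions, not prescriptions.

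Section 7 describes the outcome differently, twice. The opening of the 12-month analysis names, besides new AF diagnosis, "new prescriptions for 1) anticoagulants and 2) other AF-related medications". The next paragraph sets out Fisher's exact test and multivariable logistic regression for AF diagnosis, then extends the same analysis to anticoagulant prescriptions and to "new prescription of other AF-related medications".

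**The concern.** Section 7 is where the SAP attaches a statistical method to each outcome. If a programmer builds the 12-month table from that section, the outcome is a pharmacy fill and nothing else. A participant who had a cardioversion, an ablation or an AF admission but no qualifying fill would count as a non-event, although Sections 1, 3 and 5 make that person an event.

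The study's stated aim is to show that screening changes treatment as well as detection, and this is one of the few 12-month measures of treatment. With two descriptions of the outcome in one plan, the choice between them could be made after the data are seen.

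**Working it through.** No arithmetic applies to the size of this point. The documents give no expected rate, effect size or power for this endpoint. The only 12-month power statement (7% against 2%, 2,000 against 4,000, more than 99% power) concerns AF diagnosis. Recomputing it by a two-proportion normal approximation gives more than 0.9999, which agrees, but it has no bearing here. The check is therefore a comparison of text.

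**Step 1. Components, side by side.**

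| Component | SAP Sections 1, 3 and 5 | SAP Section 7, 12-month analysis |
|---|---|---|
| Antiarrhythmic drug | included, with beta-blockers and calcium channel blockers excluded | included as a medication; class not defined |
| Cardioversion | included | not named |
| Ablation | included | not named |
| Admission with AF as primary diagnosis | included | not named |

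The definition has four components and the analysis text has one, so 4 − 1 = 3 components have no 12-month comparison named in the methods.

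**Step 2. Is it a single slip?** No. The two paragraphs of Section 7 use the same restriction: "other AF-related medications" in the list of outcomes, and the singular prescription wording where the tests are assigned.

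**Step 3. Does another part of the SAP supply the missing test?**

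- Cardioversion and catheter ablation reappear in Section 5 under Other Endpoints (items 49 and 50). No comparison is attached to them.
- The hospitalisation analyses at 3 years cover all-cause and bleeding admissions. An AF admission would be counted among the all-cause ones, but not separately and not at 12 months.
- The descriptive-statistics paragraph of Section 7 summarises every endpoint. Its between-group tests concern characteristics at enrolment, not outcomes.

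So nothing outside the 12-month paragraphs gives a method for these three components at 12 months.

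**Step 4. Can the defined endpoint be built from the listed data?** Yes. Section 5 already lists antiarrhythmic fills (item 65), cardioversion, catheter ablation and Maze procedure (items 49 to 51), and hospital admissions with date and primary diagnosis.

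**The case against.** The best reply is that Section 7 is merely using shorthand. Nothing in the SAP says that it overrides Sections 3 and 5. Section 5 is where endpoints are defined, and Secondary Analysis 6 is itself an instruction to compare the full set. The list of 12-month outcomes in Section 7 is worded as what the analysis will include, which is not exclusive. The section is also incomplete elsewhere: it gives no method for 12-month utilisation or for 12-month time to AF diagnosis, both of which are listed in Section 3. A careful analyst might therefore apply the Section 5 definition anyway.

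Much of this stands. It shows that the broader endpoint was probably intended, and it rules out saying that the SAP has replaced its endpoint. It does not remove the contradiction. For utilisation Section 7 is silent, whereas here it names an outcome, and that outcome differs from the defined one in the sentence that assigns the test.

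A reader might also infer that Section 7 drops the exclusion of beta-blockers and calcium channel blockers, so that fills for other conditions would flood the count. The documents do not support that. The exclusion is not repeated in Section 7, but it stands in Sections 1, 3 and 5, and Section 5 lists beta-blocker, calcium channel blocker and antiarrhythmic fills as separate variables. Nor is this a cohort selected for hypertension: that diagnosis qualifies someone only together with diabetes, as one of several alternative routes.

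**Conclusion.** The inconsistency is real. Followed literally, Section 7 does not answer Secondary Analysis 6, because three of the four components have no stated 12-month comparison. It is a contradiction between sections of the SAP rather than a missing detail.

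Its reach is limited.

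- It concerns one secondary endpoint. The primary 4-month comparison of immediate with delayed monitoring is unaffected.
- The omitted components are still collected and described, so no information is lost. What is missing is their comparison as part of the defined endpoint.
- The four-part definition is in the SAP only. The protocol's objective speaks of AF-specific therapies without listing components, though that is still wider than prescriptions, and among treatments its secondary endpoints name only starting anticoagulation.
- The effect on the estimate cannot be calculated. It would need the 12-month rate of each component in each cohort and the overlap between components, and the documents give none of these.

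A reader might go further and argue that an AF admission is utilisation rather than therapy and must be split off. The SAP includes it in the endpoint in all three definitions. Splitting it off would be a preference about the definition and is not needed to resolve the inconsistency.

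**What to change.** In both places in Section 7 (the list of 12-month outcomes and the sentence extending the tests to them), replace the medication wording with the Section 5 definition, including its exclusion of beta-blockers and calcium channel blockers. State that the outcome is the proportion with any of the four components within 12 months of the monitored participant's enrolment. Compare it by the Fisher's exact test and logistic regression already specified, intention-to-treat first and per-protocol second. The components may also be reported descriptively, one by one.

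The cost is a wording change to the SAP, best made before the 12-month outcome data are examined. It needs no new data, no change to the sample size and no change to the protocol.
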